group differences are moderated by gender, baseline menthol cigarette use (not SREC flavor), and nicotine dependence level, and also examine the degree to which baseline characteristics might predict success on these outcomes. We will use descriptive statistics to report the frequency of flavor choice, how that varies over time, by condition, and by level of reduction.

We will also be weighing all returned SREC pods and will also be able to develop a measure of SREC use per week based on SREC pod weight.

**Aim 2. Examine whether reductions in conventional cigarette use and uptake of SREC are associated with changes in health and biomarker variables.** Smokers may vary in how completely they substitute SREC for their conventional cigarettes. Thus, for each participant, we will have, on a weekly basis, the number of cigarettes smoked and the number of SREC episodes or returned SREC pod weights. As indicated above, these will be modeled using mixed models for counts, which yield empirical Bayes estimates for each subject of their change across time in cigarette and SREC usage. We will examine how these change in usage estimates are associated with changes in the following variables: 1) CO level; 2) blood pressure; 3) heart rate; 4) weight (assessed baseline and at end); 5) self-report of respiratory symptoms (baseline and at end); and 6) nicotine dependence (assessed at baseline and end). For each of these continuous outcomes, we will use linear mixed models with effects of time and group (usual flavor or free choice), and group by time interaction if significant. To these models, we will add in the empirical Bayes estimates of cigarette and SREC change (obtained from the stage 1 mixed models for counts) and specifically examine the change by time interactions (and change by group by time if the group by time interaction is significant). As the empirical Bayes estimates from the stage 1 analyses have uncertainty attached to them, we will use the resampling approach advocated by Tsonka et al for using empirical Bayes estimates from a first stage analysis as covariates in a second stage model.

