**Power considerations.** The proposed sample size of 120 smokers was determined based on the primary aims. In all power calculations, we conservatively assumed an attrition rate of 10%, yielding a sample size of 108 at the end of the study. We will randomize 60 smokers to usual flavor SREC (N=54 at end) and 60 smokers to choice of flavor SREC (N=54 at end). The primary endpoint is the group difference in the rate of combustible cigarettes used at the 12-week timepoint. We will model this outcome across time in a mixed Poisson model. Based on data from our prior study of dual users of cigarettes and e-cigarettes and current experience, the average rate of smoking is expected to be between 11 to 15 cigs/day. With the proposed sample of 54/54 at the 12-week timepoint, we have power of .8 for a two-tailed hypothesis test to detect a relative risk of .75 (reduction to 8.2 cigs/day in the flavor choice group relative to 11 cigs/day in the usual flavor group or reduction to 11.25 cigs/day in choice vs 15 cigs/day in usual flavor). We note that these are conservative estimates of power as these calculations only consider data from the 12-week timepoint, whereas our model will include the longitudinal data from the 12 weeks. In addition, we expect significantly greater reductions in the flavor choice group than we are estimating here given expectations of greater engagement and adherence in the choice group, but these power considerations build in the likelihood that reductions are not sustained. Thus, we believe that these are conservative estimates. In terms of the binary outcome of abstinence at the final 12-week timepoint, we have power = 0.8 for a comparison of abstinence rates of 31.5%

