(flavor choice) vs 10.% (usual flavor) for a two-tailed hypothesis test. Again, this is conservative as it is a two-tailed test and only considers data at the 12-week timepoint and attrition of 10%. Thus, we have good power to detect meaningful differences in both smoking rates and smoking/abstinence classification. In addition, given the ample EMA data, we will be able to examine how satisfaction/pleasure from SREC is associated with adherence to SREC and reduction in cigarette rate. For aim 2, which will examine associations between changes in SREC usage and change in health outcomes, again, we conservatively consider power at one timepoint. For this, with the sample size of 108 (allowing for 10% attrition), we can detect a correlation of .262 with power of .8 on a two-tailed hypothesis test. This level of association is between a small and medium effect size, and in line with correlations that we have observed in our prior studies.

For aim 3, in terms of the EMA data, given that we are including smokers who smoke 3+cigs/day; we are likely to have many events per day over the week to sample. Even with 3 smoke events/ day; plus 5 random a day – that is likely to give about 30 random events and at least 21 smoke events at baseline across 120 participants, providing ample data for within- and between-subject analyses. As an example, we can consider power for comparing responses from smoking reports to random prompts using simulation. Based on our current data, we assumed an intraclass correlation coefficient between 0.3 to 0.4, and considered power for a binary outcome (e.g., alone vs not alone). We simulated 1000 datasets and estimated a logistic mixed effects model including a random subject effect and fixed effect comparing random prompts and smoking reports. Power is determined as the proportion of datasets in which the null hypothesis of no difference between random prompts and smoking reports is rejected. Under these assumptions, power exceeded 0.8 for an odds ratio of 1.2.

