For aim 4, during the switch week we are likely to see the same number of random events (and the SREC events and conventional cigarette events may both occur). Thus, we can examine what are the situations in which they still smoke or contexts in which they can switch. If we assume, conservatively, 20 smoking events and 10 SREC events, with 108 subjects (allowing for 10% attrition) and an ICC between 0.3 and 0.4, we can detect an odds ratio of 1.25 with power = .8 on a two-tailed .05 test. Thus, we have excellent power to detect rather small differences for within-subject comparisons involving cigarette vs SREC reports, even with a modest number of SREC events per person. Power for comparisons to random prompts will be even better.

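### Aim 2 looks for an arm difference in the use–health association only when mean health change differs by arm, which is a different hypothesis; the loss of power falls on a secondary question and ranges from negligible to about 72 points

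*Combined protocol and SAP*

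**What the plan says.** Section 9.0, Aim 2, builds the models in two steps. For each continuous health outcome (CO, blood pressure, heart rate, weight, respiratory symptoms, nicotine dependence), "we will use linear mixed models with effects of time and group (usual flavor or free choice), and group by time interaction if significant". Next, "To these models, we will add in the empirical Bayes estimates of cigarette and SREC change", taken from the first-stage count models. The analysts will then "specifically examine the change by time interactions (and change by group by time if the group by time interaction is significant"). Change by time is therefore always examined, while change by group by time is examined only after a significant group-by-time result. No other section provides an unconditional look at the three-way term, and no significance level is given for the condition.

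The hypothesis stated for Aim 2 in section 3.0 concerns the overall association only: more complete substitution should go with larger falls in CO and respiratory symptoms. The Aim 2 power statement in section 12.0 covers the same association: "we can detect a correlation of .262 with power of .8 on a two-tailed hypothesis test".

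**The concern.** Group by time compares mean health change between arms. Change by group by time compares the slopes of health change on usage change. Two arms can have the same mean fall in CO and quite different use–CO slopes, or different mean falls and a common slope. Making the second test depend on the first lets a result about means decide whether slopes are looked at.

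What is at stake is the reading of the pooled association. If the slope exists mainly in one arm and the mean changes happen to be similar, the plan yields one pooled slope, diluted, with nothing to show that the arms differ. The opposite error of focus is also possible. If all six outcomes had equal mean change and were independent, at least one would meet the condition by chance in 1 − 0.95^6 = 26% of trials, and the arm comparison of slopes would then be made for whichever outcome that was.

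**Working it through.** **Inputs from the documents.** Section 12.0 "conservatively assumed an attrition rate of 10%, yielding a sample size of 108 at the end of the study", with equal arms: "We will randomize 60 smokers to usual flavor SREC (N=54 at end) and 60 smokers to choice of flavor SREC (N=54 at end"). The only Aim 2 effect size is r = .262 with power .8, two-tailed. The only significance level stated anywhere is in the Aim 4 power statement: "we can detect an odds ratio of 1.25 with power = .8 on a two-tailed .05 test".

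**Assumptions.** The condition is tested at two-sided .05, with .10 as the range. The documents give no arm difference in association, so pairs of within-arm correlations are illustrative.

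**Step 1: the plan's own figure.** With N = 108 and r = .262, the noncentrality is .262 × √108 / √(1 − .262²) = 2.82, and the noncentral t gives power .798. Fisher's z gives Φ(0.268 × √105 − 1.96) = .785. The stated .8 is reproduced, at two-sided .05 (one-sided Fisher z would give .865).

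**Step 2: the bound when mean changes are equal.**

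P(detect) = P(condition met and three-way term significant) ≤ P(condition met) = α.

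So P(miss) ≥ 1 − α: 95% at .05 and 90% at .10. This needs only that the group-by-time test holds its nominal size. If the two tests were independent, P(miss) = 1 − α × power. For example, 1 − .05 × .8 = 96%.

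**Step 3: simulation with equal mean changes.** Change scores, 54 per arm, 20,000 trials per row. In arm g, y = r_g·u + √(1 − r_g²)·e, with u and e standard normal. The condition is a two-sample t test on y. The three-way term is the t test of the slope difference on 104 df.

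| Within-arm r | Condition met | Three-way power, no condition | Three-way power as planned |
|---|---|---|---|
| 0 vs .262 | 5.0% | 27% | 1.4% |
| 0 vs .5 | 4.8% | 76% | 3.5% |
| .1 vs .6 | 5.1% | 79% | 3.9% |
| −.1 vs .5 | 4.7% | 90% | 4.2% |
| 0 vs .7 | 4.9% | 98% | 4.8% |
| −.3 vs .6 | 4.9% | 99.9% | 4.9% |

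With the condition at .10 and r of 0 vs .5, planned power is 7.3%, a 92.7% miss rate.

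Hand check of the second row: the average residual variance is (1 + .75)/2 = .875, and the SE of the slope difference is about √(.875 × 2/51) = .185. Then .5/.185 − 1.98 ≈ 0.72, giving power of about 76%.

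**Step 4: unequal mean changes, r of 0 vs .5.** There are two ways for the means to differ.

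(a) An arm difference in mean health change unrelated to the slopes (3,000 trials; repeat runs agree within 2 points):

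| Mean arm difference | Condition met | Power as planned |
|---|---|---|
| 0.2 SD | 17% | 12% |
| 0.3 SD | 34% | 25% |
| 0.5 SD | 73% | 56% |

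(b) Equal intercepts and the same non-zero mean usage change μ in both arms. The slope difference then itself creates a mean difference of 0.5 × μ SD:

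| μ (SD of usage change) | Condition met | Power as planned |
|---|---|---|
| 0.5 | 26% | 19% |
| 1 | 73% | 55% |
| 1.5 | 97% | 74% |
| 2 | 99.9% | 76% |

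Against about 76% without the condition, the loss runs from 76 − 76 = about 0 points to 76 − 3.5 = about 72 points.

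**Limits.** A single change score stands in for the planned mixed model. Table 2 schedules CO, blood pressure and heart rate at eight visits (weeks 1, 2, 3, 4, 6, 8, 11, 14), so the chance of meeting the condition for those outcomes (73% at 0.5 SD here) is only approximate. Uncertainty in the empirical Bayes estimates is ignored. Neither affects the bound in Step 2.

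**The case against.** The strongest reply is that the conditional term is not what Aim 2 is about. The hypothesis, the power statement and the change-by-time test all concern the overall association, and that test is always run. No section predicts that the association differs by arm, and moderators are named only for Aim 1. A reader might infer that the main Aim 2 analysis is compromised, or that the plan takes a non-significant group-by-time result as evidence of a common slope. The documents support neither inference: change by time is unconditional, and section 9.0 makes no claim about a common slope.

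A second reply is that the 95% figure is only 1 − α under equal means, with an α the plan does not state. That is right. A reader might take 95% as the general miss rate, but the documents do not make equal mean change the expected case. Section 6.1 coaches both arms toward a reduction of at least 75%, so mean cigarette change should be away from zero, and Aim 1 predicts a larger reduction in the choice arm. Under equal intercepts, Step 4(b) shows that the loss can vanish. The documents give no SD for usage change, so the trial cannot be placed within that range.

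Third, correlations of 0 and 0.5 are not the plan's. At 0 versus its own .262, the unconditional test would still miss about 73%. This stands, and it argues for estimates with intervals rather than another significance test.

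Finally, holding back unpowered three-way terms is a defensible form of parsimony. But parsimony does not justify this particular trigger, whose effect on power depends on quantities other than the slope difference being sought.

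**Conclusion.** The point holds as a defect in a secondary, exploratory part of Aim 2. The plan conditions a question about slopes on a test about means. When mean health changes are equal, a real arm difference in the use–health association is missed at least 95% of the time with the condition at an assumed .05, or 90% at .10. Away from equal means, the cost at 54 per arm and illustrative correlations of 0 versus 0.5 lies anywhere between about 0 and about 72 points of power. At 0 versus .262 there is little power to lose, since the unconditional test has about 27%. The 0-to-72 range rests on a change-score approximation and on assumed correlations; the 1 − α bound rests only on equal means and a correctly sized group-by-time test. The hypothesized overall association remains tested in every case. The change is worth making because it determines whether Aim 2 can say anything about arm differences in the association, and it costs almost nothing.

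**What to change.** In section 9.0, Aim 2, remove both conditions on significance: the one on including group by time and the one on examining change by group by time. Keep group by time in every Aim 2 model; the three-way term needs it as a lower-order term in any case. For each outcome and each use measure, report the use–health slope in each arm and the difference between them with a 95% confidence interval. Label these results exploratory and read them as estimates. Leave change by time as the main Aim 2 test.

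The cost is a wording change and some additional model terms, with no new data or visits. The downside is multiplicity. Six outcomes by two use measures gives about 12 interaction estimates. If each were tested at .05 and all were independent, the chance of at least one false positive would be 1 − 0.95^12 = 46%, which is why they should not be presented as confirmatory tests.

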## 6.0 Study Design and Procedures

All human subjects research will be conducted at the Institute for Health Research and Policy at UIC. Some portions of the data analyses conducted by Co-I [name] may take place at the University of Chicago. [name] role involves guiding the data analyses and writing up results for presentation and publication. [name] will only have access to a deidentified dataset and will not have any responsibility for recruitment, enrollment, consent, or data collection, and will never be able to access any participant contact information.

**Design Overview.** Participants will complete baseline assessments and a one-week EMA wave while they continue their usual pattern of cigarette use. After their first EMA week, participants will be randomized (within sex) in a 1:1 ratio to receive either SREC pods in their usual flavor (n=60) or pods in their choice of flavor (n=60). Participants assigned to the flavor choice condition can select from the four available SREC flavors (tobacco, menthol, watermelon, and blueberry) based on their preference and satisfaction with the flavor throughout the trial. All participants will receive brief behavioral counseling about reducing their cigarette use and switching to the SREC. After an initial week of using SREC and reducing the number of cigarettes smoked, participants will complete another EMA week assessing patterns and responses to use of both products. Participants will receive 12 weeks of SREC pods; complete daily reports of product use along with bi-weekly check-ins through the end of the 12-week trial, and then complete a one-month follow-up. Female participants of childbearing age (55 years old and younger) will provide urine for a required pregnancy test every 5 to 6 weeks and will be removed from the study if the test indicates a pregnancy. The total study duration for participants is 18 weeks. Table 1 shows the timeline of assessments, procedures, and modality.

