Adverse Events (e.g., throat irritation, nausea)			x	X	x	x	x	x	x	x	x	x	x	x		

A. A **Comprehensive questionnaire** (baseline and 14-Week End of Treatment visits) will be completed in-person to assess key constructs [e.g., sociodemographics, tobacco and nicotine use (history, dependence, attitudes, motivations, intentions, perceived harm), tobacco environment, cessation history and intentions, and other substance use]. Each questionnaire will take approximately 30 - 40 minutes to complete. Shorter **brief surveys** (5-7 minutes to complete) will be completed at weeks 2, 3, 4, 6, 8, and 11. These measures serve as important descriptors of our sample, serve as covariates or moderators in our analyses, and serve as predictors of success in reducing cigarettes and switching to SREC over time.

B. A **daily use survey** completed online via REDCap from an emailed or texted survey link starting at the week 2 visit through the week 14 visit (over the 12 treatment weeks) to assess the use of cigarettes, SREC, and any other e-cigarette/nicotine vaporizer. Each of these surveys will take about 1 minute to complete. This brief survey will serve as an indicator of change in patterns of use as well as a way for the Clinical Interviewer Staff to track progress with cigarette reduction and to monitor nicotine exposure during the treatment phase. Daily surveys ask about the number of cigarettes smoked and the number of SREC or other e-cigarette episodes on the previous day (an episode is defined as 15 puffs or a period lasting about 10 mins). We also ask if the participant finished a pod on the previous day.

C. **Two, week-long waves of EMA data collection** using a **study provided smartphone**, the first wave will take place immediately following completion of the baseline questionnaire (week 1 visit through week 2 visit), and the second wave will take place starting at the week 3 visit through the week 4 visit. The first week of EMA provides the baseline comparison with combustible cigarettes to the second EMA wave when participants will have one week of experience with using the SREC and some practice cutting down on their cigarette smoking. Each EMA wave will cover 7 consecutive days, ensuring both weekday and weekend sampling.

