We will provide a study smartphone with the custom app installed to each participant. The app is specifically developed for the EMA data collection, which will conduct brief tobacco use interviews through random prompts and participant-initiated recordings of cigarette/SREC/e-cigarette use episodes. The EMA app will “beep” randomly between 5 -7 times a day during waking hours, and ask questions about the participant's daily experiences, such as what they are doing, who they are with, and how they are feeling. It will also ask about cigarette/SREC/e-cigarette use and use of alcohol and marijuana. These interviews will take about two minutes each to complete. Participants also initiate an interview on the app each time they smoke a cigarette or use the SREC device (or other e-cigarette/vaporizer). Each of these interviews also take about 3 minutes to complete. When participants event-record cigarette/SREC use, they respond to questions about their immediate context and mood, but also answer questions related to their cigarette/SREC use. First, they will indicate which product they are using, and subsequent questions are tailored to that product. They will be asked about quantity (e.g., how many cigarettes, how many puffs), how much they wanted to use that specific product, how strong their urge was to smoke (asked regardless of product used), how much they “craved” a cigarette (asked regardless of product used), and potential withdrawal and nicotine-related symptoms (restless, impatient, hungry, sick, buzzed). They will also be asked about “throat hit” and any throat irritation. Other withdrawal symptoms are already included in our mood assessments (e.g., irritable, trouble concentrating, anxious). We will train participants individually on how to use the app. Given the ubiquity of smartphones, participants rarely have difficulty completing prompts. After the first day, the trainer will call participants to assess compliance and assist with problems. Research staff will be available via phone and email throughout the week to respond to research or technology issues with the phone or app.

D. **Semi-structured, debriefing interview** (see Appendix: ED Debriefing Interview) following each wave of EMA data collection this interview will be conducted to assess compliance with the EMA protocol, reactivity to carrying the ED, a review of data quality, and obtain feedback on the EMA data collection experience. The debriefing interview will take about 20 minutes.

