**Aim 3: Examine smokers' subjective responses to SREC in real time, and whether these responses are associated with cigarette reduction.** Levels of satisfaction, pleasure, mood change following use, and withdrawal symptoms will be assessed via EMA during the second week of SREC use. Level of satisfaction, pleasure, and mood will be assessed following each use of SREC (event report), and withdrawal symptoms will be assessed both during random times and following SREC use. We will also descriptively examine how the SREC flavor may be associated with adherence and overall level of subjective responses. We will use linear mixed models to compare groups in terms of the EMA subjective reports and withdrawal symptoms. Also, using the empirical Bayes estimates from these linear mixed models of EMA-reported subjective experience and withdrawal, we will examine whether these predict longitudinal changes in cigarette use over the following weeks, which will be modeled using a Poisson mixed model including effects of group, time (and group by time if significant). We will specifically examine the effects of satisfaction and withdrawal on cigarette use, both as main effects and as interactions with time if significant. Again, we will follow the resampling approach to account for the uncertainty of the empirical Bayes estimates.

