**Aim 4. Examine how patterns of use (e.g., contexts, timing) and subjective experience with SREC, differ from conventional cigarette use, and whether differences are associated with success in switching to SREC (giving up or reducing combustible and using SREC).** We will have baseline EMA data on smoking events and random time sampling of urges, mood, satisfaction with smoking, as well as context. Then we will have a week of EMA data on the second week of the instructed switch to SREC. We will compare EMA data during baseline to the SREC switch week on the following within subject factors: context of use (alone, with others; location – home; work; in public; presence of other smokers; time of day (e.g., first cigarette of the day); mood prior to use; mood after use; urge prior to use and at random time; satisfaction after use). We will use three-level (observations within weeks within subjects) linear mixed models for continuous outcomes (mood), logistic mixed models for binary outcomes (context), and survival mixed models for time to an event (first cigarette of the day). The main independent variable will be the indicator of EMA week (baseline/switch week) to test whether the outcomes vary by EMA week. We will also control for group (usual flavor/flavor choice) and examine whether the effect of EMA week varies by group. Analyses will also include sex and prior menthol use as covariates.

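### Aim 3 compares the arms on switch-week EMA ratings without the pre-randomisation EMA value as a covariate, which gives up precision of a size the documents do not fix

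*Combined protocol and SAP*

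**What the plan says.** Section 3.0 states an arm hypothesis for Aim 3: the flavor choice group should report more satisfaction, pleasure and mood enhancement than the usual flavor group. Section 9.0 (Aim 3) says the ratings "will be assessed via EMA during the second week of SREC use". Satisfaction, pleasure and mood are rated after SREC use; withdrawal is rated at random times and after SREC use. The comparison is one sentence: "We will use linear mixed models to compare groups in terms of the EMA subjective reports and withdrawal symptoms". No baseline EMA value is named as a covariate. Empirical Bayes estimates from these same models then serve as predictors of later cigarette use.

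A baseline EMA week exists. Section 6.0 says: "After their first EMA week, participants will be randomized (within sex) in a 1:1 ratio". Section 6.3 (item C) describes its role: "The first week of EMA provides the baseline comparison with combustible cigarettes to the second EMA wave". Section 9.0 (Aim 4) describes its content: "We will have baseline EMA data on smoking events and random time sampling of urges, mood, satisfaction with smoking, as well as context". Aim 4 fits three-level models to both weeks, with EMA week as the main factor and sex and prior menthol use as covariates. On the arms it says: "We will also control for group (usual flavor/flavor choice) and examine whether the effect of EMA week varies by group". Its listed outcomes are context, time of day, mood before and after use, urge, and satisfaction after use. Withdrawal and pleasure are not listed by name, although section 6.3 notes that some withdrawal symptoms sit inside the mood items.

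**The concern.** People differ in how positively they rate mood and satisfaction and in how much withdrawal they report. Where those differences persist from one week to the next, they add variance to an arm comparison made on second-week ratings alone, and the person's own first-week mean can remove part of it. That mean is measured before randomisation, so adjusting for it cannot bias the arm effect, and it is already being collected. At stake is the precision of the Aim 3 arm contrast, and a choice between adjusted and unadjusted results that the plan leaves open until the data are in.

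**Working it through.** **The plan's own figure.** Section 12.0 gives one Aim 3 power figure: above 0.8 for an odds ratio of 1.2, comparing smoking reports with random prompts on a binary item. With 120 people, 30 random and 21 smoking reports each, two-sided 0.05, and the information for a random-intercept logistic model approximated analytically, power is 0.84 to 0.87 at a 50% event rate (ICC 0.4 to 0.3) and 0.79 to 0.82 at a 30% rate. The event rates are assumed. The stated figure is consistent with this, but it is a within-person contrast and says nothing about the comparison between arms.

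**Inputs for the arm contrast.**
- From section 12.0: 54 per arm at study end; about 30 random and at least 21 smoking reports in the first week; ICC 0.3 to 0.4, stated for a binary context item and carried over here as an assumption; two-sided 0.05, stated for Aim 4.
- Assumed, not in the documents: 10 to 30 second-week reports per person (m); 80% power for the unadjusted contrast; person-level between-week correlation ρ of 0.3, 0.5 or 0.7.

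**Formulae** (variance of a single rating set to 1; m₁ = first-week reports, 21 to 30).
- Variance of the second-week person mean: V = ICC + (1 − ICC)/m.
- Variance of the first-week person mean: V₁ = ICC + (1 − ICC)/m₁.
- Correlation of the two means: r = ρ × ICC / √(V × V₁).
- Baseline adjustment multiplies the variance by 1 − r².
- A week-by-group interaction, read as a change score, has variance V + V₁ − 2ρ × ICC in place of V.
- Adjusted power = Φ(2.802/√(1 − r²) − 1.960), where 2.802 = 1.960 + 0.842 corresponds to 80%.

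**One case in full** (ρ 0.5, ICC 0.3, m = 20, m₁ = 30). V = 0.3 + 0.7/20 = 0.335. V₁ = 0.3 + 0.7/30 = 0.323. r = 0.15/√(0.335 × 0.323) = 0.456, so 1 − r² = 0.792. Power = Φ(2.802/0.890 − 1.960) = Φ(1.19) = 88%. Change score: 0.335 + 0.323 − 0.300 = 0.358, and power = Φ(2.802 × √(0.335/0.358) − 1.960) = Φ(0.75) = 77%.

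**Results over all combinations.**

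| ρ | r | 1 − r² | Baseline-adjusted power | Week-by-group power |
|---|---|---|---|---|
| 0.3 | 0.26–0.29 | 0.92–0.93 | 83% | 64–66% |
| 0.5 | 0.43–0.48 | 0.77–0.82 | 87–89% | 76–78% |
| 0.7 | 0.60–0.67 | 0.56–0.64 | 94–96% | 89–93% |

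At ρ 0.5 with 30 first-week reports, the difference detectable with 80% power falls from 0.31–0.37 to 0.27–0.33 SD of a single rating. In sample-size terms, ρ 0.5 is worth 108/0.82 to 108/0.77, or about 132 to 140 completers instead of 108.

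**Dependence on the starting power.** With the two weekly means correlated at 0.45, the gain is 9.3 to 9.8 points from a start of 50 to 70%, 8.0 points from 80% and 5.3 points from 90%.

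**The case against.** The strongest reply is that the pairing is already used. Aim 4 models both weeks, includes arm, sex and prior menthol use, and tests whether the week effect differs by arm on overlapping outcomes. This stands against any reading that the plan ignores the baseline week. It does not close the gap. The interaction behaves like a change score and has less power than baseline adjustment at every correlation tried; below ρ of about 0.5 it has less power even than the unadjusted contrast. Withdrawal and pleasure are also missing from the Aim 4 list.

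Four further objections stand in part.
- The ICC belongs to a binary context item, so carrying it over to mood, withdrawal and satisfaction is an assumption.
- The first week holds cigarettes only. SREC satisfaction and pleasure have no same-product baseline, and the post-cigarette rating is a proxy of unknown correlation, so the gain there may be smaller.
- The first-week EMA mean is neither the only baseline measure nor a complete remedy. Table 2 also collects satisfaction, withdrawal and mood by questionnaire at week 1, and section 6.3 (item A) says questionnaire measures serve as covariates, though Aim 3 names none. At ρ 0.3 adjustment removes only 7 to 8% of the variance, while going from 10 to 30 reports removes 13% at ICC 0.3 (0.370 to 0.323) or 9% at ICC 0.4 (0.46 to 0.42).
- Adding the covariate to the existing models would change the empirical Bayes predictors from a person's level of response into a residual from baseline. The fix has to avoid this.

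**Conclusion.** The point holds as a matter of efficiency. As written, the Aim 3 arm comparison names no baseline EMA term although one is collected before randomisation, and Aim 4 does not replace it. Under the stated assumptions the gain from an 80% start is about 3 points at ρ 0.3, 7 to 9 at ρ 0.5 and 14 to 16 at ρ 0.7.

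A reader might infer that the plan loses a definite amount, such as about 8 points of power. The documents do not support a single figure: it would need both an unstated between-week correlation and an unstated starting power. A reader might also infer that the comparison is biased. It is not, because randomisation protects the unadjusted contrast. No power claim in the plan is contradicted, and the primary endpoint lies in Aim 1. The 54 per arm is the end-of-study figure; more people may contribute to the second EMA week, which falls early in treatment.

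**What to change.** In the Aim 3 arm-comparison models, add the participant's first-week EMA person mean of the same item as a covariate for mood and withdrawal, matching random prompts to random prompts. For post-SREC satisfaction and pleasure, use the post-cigarette rating as a declared proxy; ratings of mood or withdrawal made after SREC use likewise have only a post-cigarette counterpart. Keep the arm coefficient as the test.

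Fit the models that supply the empirical Bayes predictors of cigarette reduction separately, without this covariate, so that their meaning does not change.

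State how the covariate is filled in for participants with no first-week data; simple mean imputation that ignores arm is enough if they are few, as expected. The cost is a short addition to section 9.0, one extra model per outcome and that imputation rule. No new data are needed.
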